1.4. Rationale for the Study

Sickle cell disease is a chronic debilitating disease characterized by vaso-occlusive episodes, hemolytic anemia, and progressive vascular injury to multiple organ systems.²² Chronic anemia is associated with decreased physical activity, poor sleep quality, cognitive impairment, fatigue and reduced QOL in patients with SCD. Given the negative impact of anemia on physical activity, sleep, and QOL in SCD and other hemolytic disorders, treatment of anemia represents a rational approach to improve measures of daily functioning. Voxelotor has been well tolerated in adult and pediatric participants aged ≥ 4 years and has shown rapid, significant, and sustained improvement in Hb and hemolysis measures over that achieved from standard-of-care therapy including HU;³⁷ therefore, exploration of the effect of voxelotor in participants who may have the greatest potential to benefit from a disease-modifying therapy is warranted. Actigraphy provides an objective measure of physical function and has been successfully used in prospective interventional studies to assess the impact of pharmacologic treatments on physical activity, sleep, and QOL measures. The rationale for this study is based on the potential for voxelotor, through its effects on anemia and hemolysis, to improve measures of daily functioning, as assessed by actigraphy in participants with SCD and moderate anemia.

1.5. Dose Rationale

Voxelotor is indicated for the treatment of SCD in adults and pediatric patients 12 years of age and older. This indication was approved under accelerated approval based on increase in Hb. The approved dose of 1500 mg taken orally once daily is supported by results of the pivotal Phase 3 Study GBT440-031 in adults and adolescents with SCD demonstrating: (1) a statistically significant and clinically meaningful increase in mean Hb level of 1.1 g/dL and reductions in clinical markers of hemolysis observed with voxelotor 1500 mg compared to placebo and which were more robust than those observed with voxelotor 900 mg; (2) a favorable safety profile with absence of concerning exposure-related safety findings³⁷; 3) the efficacy of the 1500 mg dose in adolescents is supported by similar improvements Hb and hemolysis measures observed in the Phase 2a Study GBT440-007⁴⁰; 4) exposure-response analyses using data from both Study GBT440-031 and Study GBT440-007 demonstrating dose-dependent treatment effects of voxelotor on Hb and hemolysis measures; and 5) the majority of adult and adolescent participants receiving voxelotor 1500 mg in the GBT440-031 study achieved the intended therapeutic target of 20% to 30% mean % Hb occupancy.

2. STUDY OBJECTIVES

The objectives of this study are to evaluate the effect of voxelotor on the outcomes listed below and are considered exploratory:

- Change in daily physical activity as measured by actigraphy in adolescent and adult participants with SCD and chronic moderate anemia
- Change in sleep quality as measured by overnight actigraphy monitoring
- Change in peripheral oxygen saturation (SpO₂) as measured by overnight SpO₂ monitoring
- Change in Hb response, as defined by > 1 g/dL increase from baseline
- Change in nocturnal oxygen saturation as assessed by overnight pulse oximetry
- Patient-reported outcome (PRO) measures of physical activity, fatigue, sleep quality, pain interference, depression, anxiety, and overall function (PROMIS), and Patient Global Impression of Change (PGIC)
- Clinician global impression of change (CGIC)

2.1. Safety

The safety and tolerability of voxelotor will be evaluated.

3. INVESTIGATIONAL PLAN

3.1. Study Design

This study is a Phase 4, multicenter, open-label, single-arm study to evaluate the effect of voxelotor on daily physical activity, measured by actigraphy, in participants with SCD and

chronic moderate anemia. The study is composed of a 28-day Screening Period, a 14-day Run-in Period, a 24-week Treatment Period, and a 28-day (4-week) Follow-up Period after last dose.

This study will be conducted at approximately 10 clinical trial sites in the US. The overall study design is illustrated in the Study Schematic provided in Figure 1.

Screening Period (28 days prior to Run-in)

After signed informed consent and/or assent form has been provided, all eligibility criteria are met, and screening assessments have been completed, participants (12 to 55 years of age [inclusive]) will enter the Run-in Period.

Run-in Period (14 days)

During the Run-in Period, participants will be given a wrist-worn actigraphy device (eg, tri-axial accelerometer) to be worn continuously throughout the Run-in and Treatment Periods. Baseline measurements of physical activity, sleep parameters, and nocturnal oxygen saturations (SpO₂) will be established during the Run-in Period.

Participants will also be given a home pulse oximeter to record continuous overnight oxygen saturation during a scheduled overnight evaluation to establish baseline nocturnal SpO₂. Additionally, QOL PRO assessments for measures of fatigue, sleep interference, pain (PROMIS), and depression (Patient Healthy Questionnaire-9 [PHQ-9]) will be completed during the Run-in Period.

Treatment Period (24 weeks)

Participants will be given a wrist-worn actigraphy device (eg, tri-axial accelerometer) to be worn continuously throughout the Run-in and Treatment Periods. During the Treatment Period, actigraphy assessments of physical activity and sleep quality, and overnight pulse oximetry assessments will be performed at scheduled time points. PRO and CGIC will be assessed at scheduled study visits. The open-label Treatment Period is considered the continuous 24 weeks of voxelotor treatment from date of first dose (ie, Day 1).

Follow-up Period (28 days)

Safety assessments including the collection of AE data, vital sign measurements, physical examinations, and laboratory evaluations will be collected at scheduled study visits.

3.1.1. Study Treatment

Dosage and treatment administration are described in Section 5.

3.1.2. Study Assessments

Study procedures and assessments are described in Section 6. The timing of the scheduled procedures and assessments are provided in Appendix 1.

Safety will be assessed during the study using standard measures, including AE monitoring, clinical laboratory tests, vital sign measurements, physical examinations (PEs), and concomitant medication use. SCD-related complications will also be monitored.

3.1.3. Study Endpoints

Study endpoints are described in Section 8.1.

3.1.4. COVID-19 Risk Evaluation and Action Plan

The Sponsor, or designee, will determine a risk-evaluation plan and implement an action plan considering the need to reduce unnecessary contacts in the context of the coronavirus disease of 2019 (COVID-19) pandemic or other epidemiological emergency. Site visits may be replaced by enhanced centralized monitoring or local visits may be postponed. These methods will be described in a monitoring plan by the Sponsor, or designee.

3.2. Duration of Study Participation and Duration of the Study

Participation is expected to last up to 34 weeks, including a 4-week Screening Period, a 2-week Run-in Period, a 24-week Treatment Period and a 4-week Follow-up Period.

The study will end when the last participant's last visit occurs.

3.3. Stopping Rules

3.3.1. Early Discontinuation of the Study

The Sponsor has the right to terminate the study at any time. Reasons for terminating the study may include, but are not limited to, the incidence or severity of TEAEs in this or other studies indicating a potential health hazard to participants.

In any instance of early termination of the study, the Sponsor will notify, in writing, the investigators, regulatory authorities, and Institutional Review Boards (IRBs) and will specify the reason(s) for termination.

3.3.2. Discontinuation of Individual Participants

3.3.2.1. Withdrawal of Consent

Participants and/or their caregiver/legal representative will be informed that participation is voluntary and that they may withdraw from study at any time and for any reason. Any participant who requests to be withdrawn or whose caregiver/legal guardian requests withdrawal will be withdrawn from the study by the investigator.

3.3.2.2. Discontinuation of Study Treatment

Participants may be discontinued from study treatment for any of the following reasons:

• Participant is lost to follow-up.

Every effort should be made for the participant to return to the clinic to complete the scheduled study visits. If the participant fails to return for the scheduled study visit, a documented effort must be made to determine the reason. If the participant cannot be reached by telephone after 2 attempts, a certified letter will be sent to the participant (or participant's legally authorized representative, if appropriate) requesting the participant to contact the investigator. This information will be recorded in the study

records. Only after the documented efforts are conducted and the participant is still unresponsive will the participant be considered lost to follow-up.

- Adverse event(s)
- Discretion of the investigator
- Discretion of the Sponsor
- Pregnancy

The participant should return to the investigational site for an End of Study (EOS) visit approximately 28 days after the last dose of study treatment as indicated in Appendix 1.

4. SELECTION OF STUDY POPULATION

Eligibility will be based on assessments performed prior to receiving study drug on Day 1 in this study.

A participant will be enrolled after signing the informed consent form (ICF) or the assent form for this study. Informed consent/assent must be properly executed prior to the performance of any protocol-required assessments or procedures.

4.1. Inclusion Criteria

Participants who meet all of the following inclusion criteria will be eligible for study enrollment:

- 1. Male or female with SCA (HbSS or [HbS β^0]thal genotype)
- 2. Age 12 to 55 years, inclusive
- 3. Hb \leq 8.0 g/dL during screening
- 4. Treatment with HU therapy on study is permitted if the participant has been on a stable dose for at least 90 days before enrollment with no dose modifications planned or anticipated by the investigator
- 5. Treatment with glutamine is permitted
- 6. Treatment with erythropoiesis-stimulating agents (ESAs) is permitted if the participant has been on a stable dose for at least 12 weeks before enrollment with no dose modifications planned or anticipated by the investigator
- 7. Female participants of child-bearing potential must use highly effective methods of contraception to 30 days after the last dose of study drug. Male participants must use barrier methods of contraception to 30 days after the last dose of study drug.
- 8. Females of child-bearing potential and postmenopausal females are required to have a negative pregnancy test before the administration of study drug
- 9. Written informed consent and participant assent per IRB policy and requirements, consistent with International Council and Harmonisation (ICH) guidelines

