	8. Absolute reticulocyte count (ARC) $< 100 \times 10^9/L$
	9. Screening alanine aminotransferase (ALT) > $4 \times$ upper limit of normal (ULN)
	10. Severe renal dysfunction (estimated glomerular filtration rate < 30 mL/min/1.73 m ² by Schwartz formula) or is on chronic dialysis

	11. Known active hepatitis A, B, or C or known to be human immunodeficiency virus (HIV)-positive.
	12. Females who are breast-feeding or pregnant
	13. Major surgery within 8 weeks before enrollment. Participants must have completely recovered from any previous surgery before enrollment
	14. History of hematopoietic stem cell transplant or gene therapy
	15. Received an investigational drug within 30 days or 5-half-lives, whichever is longer, prior to consent, or is currently participating in another trial of an investigational or marketed drug (or medical device)
	16. Use of concomitant medications (eg, crizanlizumab) that confound the ability to interpret data from the study
	17. Medical, psychological, or behavioral condition that, in the opinion of the investigator, would confound or interfere with evaluation of safety and/or efficacy of the study drug, prevent compliance with the study protocol; preclude informed consent; or, render the participant unable/unlikely to comply with the study procedures
	18. Use of herbal medications (eg, St. John's Wort), sensitive cytochrome P450 (CYP) 3A4 substrates with a narrow therapeutic index, strong CYP3A4 inhibitors, fluconazole, or moderate or strong CYP3A4 inducers
	19. Symptomatic coronavirus disease of 2019 (COVID-19) infection
Concomitant	The following concomitant medications are allowed :
Medications and Restrictions	• HU (stable dose for at least 3 months before signing the ICF and with no dose modifications planned or anticipated and no sign of hematological toxicity)
	• Glutamine
	• ESAs (stable dose for at least 4 weeks with no dose modifications planned or anticipated by the investigator)
	The following concomitant medications are prohibited :
	• Sensitive CYP3A4 substrates with a narrow therapeutic range
	Strong CYP3A4 inhibitors or fluconazole
	Moderate and strong CYP3A4 inducers
	Crizanlizumab (Adakveo [®])
	Other experimental SCD therapy
Study Endpoints	All endpoints in this study are exploratory and include:
	• Change in total daily physical activity (expressed in counts per minute) from baseline to Week 10-12 and to Week 22-24

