4.2. Exclusion Criteria

Participants meeting any of the following exclusion criteria will not be eligible for study enrollment:

- 1. RBC transfusion within 3 months before initiation of study drug
- 2. Planned initiation of regularly scheduled RBC transfusion therapy (also termed chronic, prophylactic, or preventive transfusion) during the study
- 3. Hospitalization for VOC or acute chest syndrome (ACS) within 30 days prior to informed consent/assent.
- 4. More than 10 VOCs requiring hospitalization, emergency department or clinic visit within the past 12 months
- 5. Planned elective surgery within the next 6 months
- 6. Physical inactivity attributable to clinically significant musculoskeletal, cardiovascular, or respiratory comorbidities
- 7. Anemia due to bone marrow failure (eg, myelodysplasia)
- 8. Absolute reticulocyte count (ARC) $< 100 \times 10^{9}/L$
- 9. Screening alanine aminotransferase $(ALT) > 4 \times upper limit of normal (ULN)$
- 10. Severe renal dysfunction (estimated glomerular filtration rate < 30 mL/min/1.73 m² by Schwartz formula) or is on chronic dialysis
- 11. Known active hepatitis A, B, or C or who are known to be human immunodeficiency virus (HIV) positive.
- 12. Females who are breast-feeding or pregnant
- 13. Major surgery within 8 weeks before enrollment. Participants must have completely recovered from any previous surgery before enrollment
- 14. History of hematopoietic stem cell transplant or gene therapy
- 15. Received an investigational drug within 30 days or 5-half-lives, whichever is longer, prior to consent, or is currently participating in another trial of an investigational or marketed drug (or medical device)
- 16. Use of concomitant medications (eg, crizanlizumab) that confound the ability to interpret data from the study
- 17. Medical, psychological, or behavioral condition that, in the opinion of the investigator, would confound or interfere with evaluation of safety and/or efficacy of the study drug, prevent compliance with the study protocol, preclude informed consent, or render the participant unable/unlikely to comply with the study procedures
- 18. Use of herbal medications (eg, St. John's Wort), sensitive cytochrome P450 (CYP) 3A4 substrates with a narrow therapeutic index, strong CYP3A4 inhibitors, or fluconazole
- 19. Symptomatic COVID-19 infection

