5.11.1. Restrictions Regarding Usage of Concomitant Medications

Concurrent treatment with HU is allowed if the dose and regimen have been stable for at least 3 months prior to signing the ICF and with no anticipated need for dose adjustments during the study and no sign of hematological toxicity. Concurrent treatment with ESAs is allowed if the dose and regimen have been stable for at least 4 weeks with no dose modifications planned or anticipated by the investigator.

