8.2. Sample Size

Approximately 50 participants who are 12 through 55 years of age (inclusive) with SCD and chronic moderate anemia will be enrolled and treated with voxelotor in this study.

8.3. **Populations for Analysis**

All participants who receive at least 1 dose of study treatment will be included in the safety population. This is the analysis population used to summarize all efficacy and safety data.

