8.4.1. Efficacy

Actigraphy assessments will be averaged over the 14-day period during the Run-in Period, Weeks 10 to 12, and Weeks 22 to 24.

Change in actigraphy, SpO₂, and PRO endpoints will be summarized for observed values and changes from baseline using appropriate descriptive statistics.

Hemoglobin response, defined as an increase in Hb of > 1 g/dL compared with baseline, will be summarized.

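### Glutamine is the only listed allowed therapy without a stable-dose or no-planned-change condition, so a planned change during the study is not barred and could be counted in the single-arm change

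*Protocol*

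**What the plan says.** Section 4.1 of the protocol treats the three therapies in consecutive criteria:

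- **Criterion 4 (HU):** "Treatment with HU therapy on study is permitted if the participant has been on a stable dose for at least 90 days before enrollment", with the further condition that the investigator plans or expects no dose change.
- **Criterion 5 (glutamine):** "Treatment with glutamine is permitted". That is the whole criterion.
- **Criterion 6 (ESAs):** "Treatment with erythropoiesis-stimulating agents (ESAs) is permitted if the participant has been on a stable dose for at least 12 weeks before enrollment", with the same condition on planned or expected changes.

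The synopsis repeats these criteria. Its list of allowed concomitant medications has the same pattern: HU carries a condition ("HU (stable dose for at least 3 months before signing the ICF and with no dose modifications planned or anticipated"), ESAs carry one, and glutamine stands between them as a bare entry. Section 5.11.1 restricts HU ("Concurrent treatment with HU is allowed if the dose and regimen have been stable for at least 3 months prior to signing the ICF") and ESAs, and leaves glutamine out.

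Section 3.1 describes an open-label, single-arm study. Under Section 8.3 everyone who takes one dose is in the safety population, and "This is the analysis population used to summarize all efficacy and safety data". Section 8.4.1 summarises changes from baseline descriptively; for actigraphy, "Actigraphy assessments will be averaged over the 14-day period during the Run-in Period, Weeks 10 to 12, and Weeks 22 to 24".

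**The concern.** With one arm and no concurrent control, the change from baseline is the only measure of effect. Anything else that changes systematically after baseline is mixed into it. The protocol guards against this for two of its three listed background therapies and leaves the third open. A site that planned to start glutamine at about Day 1 would breach no stated rule, whereas the same plan for HU or an ESA would fail the entry criteria. In a participant who starts both drugs together, their effects cannot be separated. What is at stake is the interpretation of the all-treated summaries of activity, sleep, overnight SpO2, hemoglobin response and patient-reported outcomes.

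**Working it through.** **1. Is there a glutamine condition anywhere?**

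| Place in the protocol | HU | ESAs | Glutamine |
|---|---|---|---|
| Synopsis, inclusion criteria | 90 days stable, no planned change | 12 weeks stable, no planned change | none |
| Synopsis, allowed medications | 3 months stable, no planned change | 4 weeks stable, no planned change | none |
| Section 4.1 | 90 days stable, no planned change | 12 weeks stable, no planned change | none |
| Section 5.11.1 | 3 months stable, no expected need for adjustment | 4 weeks stable, no planned change | not mentioned |

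The gap is the same in all four places.

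**2. Does another clause close it?** Exclusion criterion 16 bars "Use of concomitant medications (eg, crizanlizumab) that confound the ability to interpret data from the study", and Section 5.11.1.1 repeats this as an on-study prohibition. Both name crizanlizumab and not glutamine. A general ban of this kind does not clearly reach a drug that the protocol allows by name. Section 5.11 also leaves prescribing to the investigator's discretion.

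**3. How long is the open interval?** From Day -14 to the Week 24 visit (Day 168) it is 14 + 168 = 182 days. To the Week 12 visit (Day 84) it is 14 + 84 = 98 days.

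**4. How large could the shift be?** The protocol gives no figure to reproduce: no glutamine effect, no uptake, and no SD for any endpoint. What follows is an illustration. The only input from the protocol is n = 50 (Section 8.2). The effects, in units of the SD of the change, are assumptions.

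- Standard error of a mean change = 1/√50 = 0.141 SD.
- Shift = (net changers / 50) × effect. Net changers are those whose change acts in one direction minus those whose change acts in the other, so equal numbers give zero.
- Net changers needed for a shift of one standard error = 0.1414 × 50 / effect, rounded up.

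| Assumed effect | One net changer | Five net changers (10%) | Net changers for one SE |
|---|---|---|---|
| 0.2 SD | 0.004 SD (0.03 SE) | 0.02 SD (0.14 SE) | 35.4, so 36 (72%) |
| 0.5 SD | 0.010 SD (0.07 SE) | 0.05 SD (0.35 SE) | 14.1, so 15 (30%) |
| 0.8 SD | 0.016 SD (0.11 SE) | 0.08 SD (0.57 SE) | 8.8, so 9 (18%) |

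**5. Hemoglobin.** Each participant whose response status (an increase above 1 g/dL) turns on glutamine moves the responder proportion by 1/50 = 2 percentage points. For the mean change, if 10% changed glutamine and the assumed effect were 0.5 g/dL, the shift would be 0.10 × 0.5 = 0.05 g/dL. That is 0.05/1.1, or about 4.5%, of the 1.1 g/dL increase cited in Section 1.5. With an effect of zero, the shift is zero.

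**The case against.** The strongest reply is that this is a choice and not a slip. Glutamine is left unconditioned consistently, and the two restricted therapies have visible reasons. Section 1.1.1 links HU to oxygen saturation, which is a study outcome. ESAs by their name stimulate red cell production, and hemoglobin response is an endpoint. No section says that glutamine affects any endpoint, so the documents show no mechanism, direction or size. Moreover, no sentence authorises a change during the study; the permission comes from an express allowance plus silence. A site could read exclusion criterion 16 as barring a planned start that would confound the data. Section 5.11 requires medication, dose and duration to be recorded, so an analysis plan can identify changers. The HU and ESA conditions do not prevent unplanned changes either.

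Much of this stands. The difference may be deliberate, although the protocol gives no reason for it. A reader might infer that the protocol contradicts itself, or that a glutamine change would inflate the voxelotor result. The documents support neither. The clauses can all be followed together, and without a stated glutamine effect one can say only that an effect could be counted, not that it would be.

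Two parts do not dispose of the point. An analysis plan can flag changers afterwards, but it cannot prevent planned changes at entry, which is the job of the eligibility and medication rules. And the general ban is too open to interpretation to replace a condition that the other two therapies carry explicitly.

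**Conclusion.** The point holds as a minor, inexpensive improvement. Glutamine alone among the three listed allowed therapies has no stability or no-planned-change condition, so a planned change between Run-in and Week 24 is not barred, and any effect of it could be counted as voxelotor effect in the all-treated summary.

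The size is unknown and may be nil. Under the assumed effects, a few net changers move a mean by a fraction of a standard error; a full standard error needs 9 to 36 of 50 changing in the same direction. These figures assume 50 participants with data and an effect fully present in the assessment windows. All endpoints are exploratory and the summaries descriptive, so no test, success criterion or decision rule is affected.

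**What to change.** In the synopsis (inclusion criterion 5 and the list of allowed medications), Section 4.1 (criterion 5) and Section 5.11.1, state: *Glutamine is permitted if the participant is on a stable dose at enrollment; no participant may have a start, stop or dose change of glutamine planned or anticipated through Week 24.* The second clause covers non-users as well as users.

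A fixed look-back, such as the 90 days used for HU, is optional. It would be for consistency only, since the documents give no glutamine-specific basis for it. If one is adopted, the site would have to confirm it from the medical record, because the history in Section 6.3 covers medications for only 30 days before screening.

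The cost is one sentence in four places and no new data collection. A few recent starters, or participants with a planned change, would be delayed or excluded. Unplanned changes are not prevented, but the records required by Section 5.11 identify them.

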Duration of Study Participation	The total duration of the study will be approximately 34 weeks.

Study Population	Inclusion Criteria:
	Participants who meet all the following criteria will be eligible for enrollment in this study:
	 Male or female participants with sickle cell anemia (SCA) (sickle hemoglobin with two sickle cell genes [HbSS] or sickle hemoglobin (S) and one beta thalassemia gene [HbS β0] thal genotype)
	2. Between 12 to 55 years of age (inclusive)
	3. Screening Hb level ≤ 8.0 g/dL
	4. Treatment with hydroxyurea (HU) therapy on study is permitted if the participant has been on a stable dose for at least 90 days before enrollment with no dose modifications planned or anticipated by the investigator
	5. Treatment with glutamine is permitted
	6. Treatment with erythropoiesis-stimulating agents (ESAs) is permitted if the participant has been on a stable dose for at least 12 weeks before enrollment with no dose modifications planned or anticipated by the investigator
	 Female participants of child-bearing potential must use highly effective methods of contraception to 30 days after the last dose of study drug. Male participants must use barrier methods of contraception to 30 days after the last dose of study drug
	8. Females of child-bearing potential and postmenopausal females are required to have a negative pregnancy test before the administration of study drug
	9. Written informed consent and/or parental/guardian consent and participant assent per Institutional Review Board (IRB) policy and requirements, consistent with International Council on Harmonisation (ICH) guidelines
	Exclusion Criteria:
	Participants meeting any of the following exclusion criteria will not be eligible for study enrollment:
	1. Red blood cell (RBC) transfusion within 3 months before initiation of study drug
	2. Planned initiation of regularly scheduled RBC transfusion therapy (also termed chronic, prophylactic, or preventive transfusion) during the study
	3. Hospitalization for vaso-occlusive crisis (VOC) or acute chest syndrome (ACS) within 30 days prior to informed consent/assent.
	4. More than 10 VOCs requiring hospitalization, emergency department or clinic visit within the past 12 months
	5. Planned elective surgery within the next 6 months
	6. Physical inactivity attributable to clinically significant musculoskeletal, cardiovascular, or respiratory comorbidities
	7. Anemia due to bone marrow failure (eg, myelodysplasia)

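### The protocol's eligibility lists and concomitant-medication rules disagree on how long an ESA dose must have been stable, and Section 4.2 omits the CYP3A4 inducers that are barred elsewhere

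*Protocol*

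**What the plan says.** **ESA stability.** Section 4.1, criterion 6, states that treatment with "erythropoiesis-stimulating agents (ESAs) is permitted if the participant has been on a stable dose for at least 12 weeks before enrollment". Synopsis inclusion criterion 6 has the same condition: ESA treatment "is permitted if the participant has been on a stable dose for at least 12 weeks before enrollment". Section 5.11.1 gives another period: "Concurrent treatment with ESAs is allowed if the dose and regimen have been stable for at least 4 weeks". The synopsis list of allowed medications matches Section 5.11.1: "ESAs (stable dose for at least 4 weeks with no dose modifications planned or anticipated by the investigator". Neither 4-week statement gives a date from which to count back. The hydroxyurea sentence just before it in Section 5.11.1 does, asking for a dose and regimen "stable for at least 3 months prior to signing the ICF".

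**CYP3A4 inducers.** Synopsis exclusion 18 ends with moderate or strong CYP3A4 inducers. The synopsis prohibited list names the same class, and Section 5.11.1.1 disallows it with voxelotor and lists examples in Table 4. Exclusion 18 in Section 4.2 begins with herbal medications and then covers sensitive "3A4 substrates with a narrow therapeutic index, strong CYP3A4 inhibitors, or fluconazole". It stops there, and inducers do not appear.

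**The concern.** These are working eligibility rules, applied at about 10 sites. Section 13.2 has each site record a checklist of inclusion and exclusion criteria, and footnote a of Appendix 1 requires eligibility to be reviewed before the Run-in Visit. A checklist built from Section 4 and one built from the synopsis would differ on inducers. A coordinator who checks ESA use against Section 5.11.1 would apply a shorter period than one who checks it against Section 4.1.

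The study has a single arm, and one of its endpoints is a hemoglobin rise of more than 1 g/dL from baseline. If a participant's ESA dose changed shortly before baseline, there is no concurrent control against which to separate the resulting hemoglobin movement from a voxelotor effect. For inducers, Section 5.11.1.1 gives its own reason for the bar: CYP3A4 is a primary route of voxelotor metabolism. A participant who passes Section 4.2 while taking an inducer would be in breach of Section 5.11.1.1 at first dose if the inducer were still in use.

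**Working it through.** The protocol gives no figure to reproduce on this point. The check compares the passages, adds date arithmetic for the ESA rules and counts the entries in Table 4.

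**ESA: the passages side by side**

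| Place | Minimum stable period | Counted back from |
|---|---|---|
| Synopsis, inclusion 6 | 12 weeks (84 days) | enrollment |
| Section 4.1, criterion 6 | 12 weeks (84 days) | enrollment |
| Synopsis, allowed medications | 4 weeks (28 days) | not stated |
| Section 5.11.1 | 4 weeks (28 days) | not stated |

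A participant stable for at least 4 but less than 12 weeks fails Section 4.1, which requires every criterion to be met, yet satisfies the medication rule.

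**ESA: size of the disagreement.** Two inputs are needed.

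- *Enrollment date.* Section 4 says "A participant will be enrolled after signing the informed consent form (ICF) or the assent form for this study", so enrollment is read here as consent.
- *Time from consent to first dose.* Section 3.1 says "The study is composed of a 28-day Screening Period, a 14-day Run-in Period, a 24-week Treatment Period". Consent can therefore fall 28 + 14 = 42 days before Day 1, at Day -42, which is also the screening day in Appendix 1. There is no Day 0, so 28 days before Day 1 is Day -28.

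The window is the span of ESA dose-change dates that one rule accepts and the other does not.

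1. Both rules run from consent at Day -42. The 12-week limit is -42 - 84 = Day -126 and the 4-week limit is -42 - 28 = Day -70. The window is 126 - 70 = **56 days** (8 weeks). It is 84 - 28 = 56 for any consent date.
2. The undated 4 weeks is assumed to run from Day 1, with consent at Day -42. The limits are Day -126 and Day -28, so the window is 126 - 28 = **98 days** (14 weeks).
3. The same assumption with consent as late as Day -14. The 12-week limit is -14 - 84 = Day -98, so the window is 98 - 28 = **70 days** (10 weeks).

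Under the second reading the 4-week period falls wholly after consent, so a dose change made during screening could satisfy it.

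**Inducers: count of Table 4**

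- Entries listed: 21 moderate + 12 strong = 33.
- Reached by Section 4.2 criterion 18 as herbal medications: St. John's wort and St. John's wort extract (2).
- Reached as strong inhibitors in Table 3: ritonavir, tipranavir/ritonavir and lopinavir, the last listed there as lopinavir/ritonavir (3).
- Not reached: 33 - (2 + 3) = **28**, among them rifampin and phenytoin. If genistein is also read as herbal, 27.

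Other criteria may catch some of the 28. Criterion 16 excludes confounding medications by judgement, and criterion 11 excludes some infections for which drugs in the table might be taken.

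**The case against.** The strongest reply is that the rules can all be obeyed at once. Anyone stable on an ESA for 12 weeks is also stable for 4. Section 4.1 requires all criteria, so a site that reads the whole protocol ends with the stricter entry rule, and Section 5.11.1 can be taken to govern use during the study rather than entry. For inducers, Section 5.11.1.1 is an unqualified bar, the synopsis states it twice, and concomitant medications are recorded from screening onward, so use should be seen before dosing. The counts measure wording rather than effect: Table 4 is a list of examples, and the 70- and 98-day windows rest on an assumed reference date. Endpoints are exploratory and summarized descriptively.

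Much of this stands. A site that applies Section 4.1 strictly would not enroll on the 4-week rule. A breach on inducers arises only if the drug is still being taken at first dose. That sites will diverge is an inference. Section 8.2 also uses enrollment alongside treatment, so reading it as consent is not the only possibility.

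The separate-purpose reading of Section 5.11.1 is weak, however. The section asks whether the ESA dose has already been stable and whether changes are planned, which is criterion 6's own condition with a different number. Its hydroxyurea sentence closely restates the entry rule in Section 4.1 (3 months before consent against 90 days before enrollment). The section appears to repeat entry conditions, and on ESAs the repetition does not match. A bar on co-administration in Section 5 does not repair an exclusion list that fails to screen for it.

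**Conclusion.** The concern holds on both parts. The protocol states two ESA stability periods, 12 weeks and 4 weeks, the second with no reference date. Exclusion 18 in Section 4.2 lacks a drug class that three other places bar.

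The 8-week difference in length comes directly from the text. The 56-day window assumes only that both periods run from the same date. The 70- and 98-day windows also assume that enrollment means consent and that the undated rule runs from Day 1. The count of 28 out of 33 describes the reach of criterion 18 within a list of examples. It is not an estimate of how many candidates would be missed.

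The document does not say how many participants use ESAs or inducers, and it gives no figure from which to size an effect on hemoglobin or exposure. No test, alpha or power is affected. The point should be fixed because sites act on these passages when they decide who enters the study.

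**What to change.** Reconcile the passages by amendment:

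- State one ESA stability period with one named reference date, in the same terms, in synopsis inclusion 6, Section 4.1 criterion 6, the synopsis list of allowed medications and Section 5.11.1.
- Make exclusion 18 read the same in the synopsis and Section 4.2, and make both agree with Section 5.11.1.1 on CYP3A4 inducers.

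Which period, which reference date and which version of exclusion 18 should stand is the sponsor's clinical decision. The cost is amendment wording. Whether any candidate's eligibility changes depends on the rule that the sponsor keeps.
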